2.4.3 Extent of Exposure and Study Treatment Compliance

Records of IP used, and dosages administered will be kept during the trial. The *duration of study treatment* is derived as the time in days from the date of first study drug application to the date of last study drug application. The *extent of exposure* in days is determined as the duration of study treatment minus the number of days without dosing. The number of days without dosing is derived from dose documentation between the date of first study drug application and the date of last study drug application. Days without dosing are days with reported non-administration.

Subjects will be asked to return all used and unused tubes/bottles at each visit. All returned tubes/bottles that had been dispensed to a subject and are returned with a broken seal will be weighed to determine the amount of the IP used.

The *amount of drug used* in grams is derived as the sum of the difference in drug weight dispensed and returned per kit. The total amount of drug used will be evaluated and also the amount used during the first week, the three weeks from Week 1 to Week 4, and the four weeks from Week 4 to Week 8.

Duration of study treatment, extent of exposure, and amount of drug used will be presented by summary tables by treatment group.

Treatment Compliance

At all on-treatment visits, the subject will be asked if he/she has used the medication as prescribed. If this is not the case, the degree and nature of noncompliance will be collected in the CRF. In addition, subjects will be asked to complete a dosing diary during the treatment period as a measure of treatment compliance.

On a daily basis in the dosing diary, if non-administration due to approved discontinuation is reported, treatment compliance is concluded, and if missed administration is reported, treatment non-compliance is concluded.

For the entire treatment period to the Week 8 visit and for the periods from Week 0 to th Week 4 visit and from the Week 4 visit to the Week 8 visit, the percentage of *treatment compliance* is defined as 100 times the duration of the respective period minus the number of days with non-compliance divided by the duration of the respective period. Treatment compliance will be categorized to less than 80% versus 80% or more and to less than 70% versus 70% or more.

For the two periods, treatment compliance, as percentage and in categories, and non-administrations will be presented by summary tables by treatment group.

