6.2 Dosing Regimen

Subjects must apply the trial product topically once daily preferable in the evening for 8 weeks to affected areas on the following body locations:

- trunk (including the neck)
- limbs, i.e., arms (including the back of the hands)
- legs (including the buttocks and the top of the feet) and
- scalp.

The face, genitals and intertriginous areas should not be treated with the IP.

Only affected areas are to be treated.

Subjects are to record the date and time of application in the subject diary.

MC2-01-C7

16 October 2018 Version 2.0

The subject should apply enough IP to treat the entire affected areas and rub in gently to ensure that the plaques are saturated with the medication. Up to 4 tubes/bottles of 60 gram will be dispensed for a treatment period of 2 weeks including the allowed visit window of 2 days. The weekly dose is not to exceed 100 g, and the treated area should not exceed 30% of the BSA. Subjects will be instructed that preferably no trial product should be applied within 4 hours of on-treatment trial visits.

In case an AE reported in one area of the body lead the investigator to the decision to discontinue treatment this will apply for treatment in general and not only to the area for which the AE was reported.

Detailed application instructions will be provided in the subject instructions.

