8.3 Analysis Populations

The analysis populations are defined as follows:

- Intent To Treat (ITT) population: all randomised subjects
- **Per Protocol (PP) population:** all subjects in the ITT population who complete the trial without any major protocol violations. The PP population will be determined and documented in blind review of the database conducted prior to un-blinding the trial database. Subjects may be excluded from the PP population if any of the following criteria are met:
 - Failure to meet key Inclusion/Exclusion criteria; i.e. violation of inclusion/exclusion criteria that according to medical judgement may impact the primary endpoint analysis
 - Usage of restricted medications/treatments; i.e. medications/treatments that according to medical judgement may impact the primary endpoint analysis
 - Nonadherence to the visit schedule at Week 8: -7/+10 days
 - Noncompliance with the trial treatment regimen; adherence to the treatment schedule defined as application of IP as specified by the investigator for at least 80% of the days from Day 1 to Week 8 visit, and at least 80% of the days from Week 4 visit to Week 8 visit
- **Safety population:** all randomised subjects who are dispensed the trial medication, excluding subjects who return all the trial medication unused.

Subjects in the ITT and PP populations will be analyzed as randomized, and subjects in the Safety population will be analysed as treated.

The ITT population will be used for the analyses of efficacy and other endpoints, while the Safety population will be used for all safety analyses. The PP population will be used in sensitivity analyses for the non-inferiority evaluations, and in a sensitivity analysis for the PCTS score evaluation.

MC2 Therapeutics

Confidential

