8.4 Estimands

The efficacy endpoints will be analyzed focusing on two different estimands:

Primary estimand (treatment-policy): the effect of initiating the treatment regimen in subjects with mild-to-moderate psoriasis, with or without any other psoriasis treatment, and whether or not the subject adhered to the treatment regimen.

Thus, for the treatment-policy estimand all available data will be used.

Secondary estimand (hypothetical-strategy): the expected effect in subjects with mild-to-moderate psoriasis if all subjects adhered to the treatment regimen and did not take any other psoriasis treatment (=treatment that according to medical judgement may improve psoriasis).

This is interpreted in the sense that subjects did not initiate other treatment that according to medical judgement may improve psoriasis, and for visits after baseline adhered to the treatment schedule defined as application of IP as specified by the investigator at the previous site visit for at least 70% of the days from baseline visit to Week 4, Week 4 to Week 6 and Week 6 to Week 8. For example, applying IP for 10 out of 14 days is considered adherence, while 9 out of 14 days is not. Thus, for the hypothetical-strategy estimand, only data at or prior to use of other treatment that may improve psoriasis according to medical judgement, and prior to non-adherence to treatment schedule is used. Missing data, data after use of other psoriasis treatment, and data after non-adherence is imputed.

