4.2.3 Per-Protocol Set

The per-protocol set (PPS) includes all subjects of the FAS who complete the trial without major protocol deviations deemed to affect the primary endpoint analysis.

If at least one major protocol deviation is observed in a subject of the FAS, the subject will be excluded from the PPS. Decisions on excluding subjects from the PPS will be taken and documented before unblinding the study.

Subjects may be excluded from the PPS if any of the following criteria are met:

- Failure to meet key inclusion/exclusion criteria; i.e. deviation of inclusion/exclusion criteria that according to medical judgement may impact the primary endpoint analysis,
- Usage of restricted medications/treatments; i.e. medications/treatments that according to medical judgement may impact the primary endpoint analysis,
- Nonadherence to the visit schedule at Week 8: 49 to 66 days.
- Noncompliance with the trial treatment regimen; adherence to the treatment schedule defined as application of the randomized IP as specified by the investigator for at least 80% of the days from Week 0 to Week 8 visit, and at least 80% of the days from Week 4 visit to Week 8 visit.

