4.4.2 Dates

The date of Visit 1 is the reference date, Day 0. Start and end dates, and the dates of last study drug application and last contact will be related to Day 0, given as *study day*. Negative study days indicate dates before Visit 1.

It is assumed that treatment in the treatment period occurs from the evening of Day 0 to the day before Visit 6 (Week 8) unless otherwise reported.

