Efficacy endpoints will be analyzed by different estimands, following a treatment-policy strategy (primary estimand) and a hypothetical strategy (secondary estimand). Only on PTCS, a while-on-treatment strategy will be followed.

According to the *treatment-policy strategy*, all available data will be used, regardless of treatment and treatment adherence. Missing data will be imputed.

According to the *hypothetical strategy*, only data will be used under the IP and while adhering to the IP. If any other psoriasis treatment is used, i.e. treatment that according to medical judgement may improve psoriasis, data during and after the period of other psoriasis treatment intake is invalid and will not be used. Furthermore, data will not be used of periods of potential non-adherence to the IP. Non-adherence will be given if the IP is applied on less than 70% of the days from Day 0 to Week 4, Week 4 to Week 6, and Week 6 to Week 8, respectively. Non-adherence to the IP is derived from days with treatment non-compliance. Missing and invalid data will be imputed.

According to the *while-on-treatment strategy*, all available data will be used with treatment within 7 days before assessment. Data without treatment within 7 days before assessment is invalid and will not be used.

Hierarchical testing applies to the primary analyses per endpoint, not to any sensitivity analyses as described below.

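### The SAP counts a day as compliant unless a miss is reported, so unreported misses can lift a subject over the 70% and 80% adherence cuts

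*SAP*

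**What the plan says.** **How the SAP counts days.** SAP 2.4.3 works from the dosing diary day by day. A reported approved discontinuation counts as compliant, and "if missed administration is reported, treatment non-compliance is concluded". The compliance percentage for a period is its length minus the non-compliant days, divided by its length. Exposure follows the same convention: "Days without dosing are days with reported non-administration". SAP 4.4.2 adds the default that "treatment in the treatment period occurs from the evening of Day 0 to the day before Visit 6 (Week 8) unless otherwise reported". No rule covers a blank diary day or a diary that is not returned.

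**Where the count is used.** SAP 5.3 states the 70% rule of the hypothetical strategy in terms of days on which product was applied, then fixes the source: "Non-adherence to the IP is derived from days with treatment non-compliance". SAP 4.2.3 sets the per-protocol criterion as "application of the randomized IP as specified by the investigator for at least 80% of the days from Week 0 to Week 8 visit", with the same 80% for Week 4 to Week 8. It does not cite the 2.4.3 percentage, but that is the only compliance percentage the SAP defines, and 2.4.3 categorises it at 80% and 70%.

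**What the protocol says.** Protocol 6.2: "Subjects are to record the date and time of application in the subject diary". Protocol 8.3 asks for "application of IP as specified by the investigator for at least 80% of the days from Day 1 to Week 8 visit". Protocol 8.4 sets 70% per interval and gives an example: "applying IP for 10 out of 14 days is considered adherence, while 9 out of 14 days is not". SAP 5.6, which lists changes from the protocol, mentions none in how adherence is counted.

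**The concern.** The protocol's thresholds concern days on which product was applied, and its diary is described as a record of applications. The SAP starts from full compliance and subtracts only reported misses. The two agree when every miss is reported. When a skipped dose leaves only a blank, the SAP scores that day as applied.

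The count decides which data the hypothetical strategy discards and is the natural basis for the 80% per-protocol criterion. These are two of the three sensitivity analyses of the primary endpoint (SAP 5.5.1), and the only two that address adherence. In a non-inferiority trial, keeping non-users of both products generally pulls a real difference between cream and gel towards zero. That weakens the analyses meant to show that poor adherence did not produce the result.

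**Working it through.** **1. The protocol's own example.** At the 70% cut of protocol 8.4, 10/14 = 71.4% is adherent and 9/14 = 64.3% is not, as the protocol states.

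**2. The same subject under the SAP.** Score = 100 × (D − reported missed days)/D. The subject applied on 9 of 14 days, so 5 were missed; b of these were not reported. D is 14, or 15 if the SAP 4.6.1 convention (end minus start plus 1) is used.

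| Unreported misses b | D = 14 | D = 15 |
|---|---|---|
| 0 | 9/14 = 64.3% | 10/15 = 66.7% |
| 1 | 10/14 = 71.4% | 11/15 = 73.3% |
| 2 | 11/14 = 78.6% | 12/15 = 80.0% |
| 3 | 12/14 = 85.7% | 13/15 = 86.7% |
| 4 | 13/14 = 92.9% | 14/15 = 93.3% |
| 5 | 14/14 = 100% | 15/15 = 100% |

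With either denominator, one unreported miss crosses the 70% cut.

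**3. The 80% criterion, if the same percentage is used.**
- Week 4 to Week 8, applied on 18 of 28 days (64.3%): with 5 of the 10 misses unreported the score is (28 − 5)/28 = 82.1%; with all 10 unreported it is 100%.
- Whole period, applied on 36 of 56 days (64.3%): with 10 of the 20 misses unreported the score is (56 − 10)/56 = 82.1%; with all 20 unreported it is 100%.

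**4. Illustration of the effect on a non-inferiority conclusion.** The documents give no rate of unreported non-use, so the shares below are assumptions.
- Inputs from protocol 8.2: 204 per active arm, SD 38, gel reduction 56 points, vehicle reduction 27 points, margin 12. With these, the power at zero true difference comes to 89.1%, against 88.9% stated.
- Assumptions: the cream is exactly at the margin in adherent subjects (56 − 12 = 44). A share c of the cream arm and g of the gel arm are complete non-users who respond like vehicle and are retained. The arm size stays at 204.
- SE = 38 × √(2/204) = 3.763.
- Difference (cream minus gel reduction) = (44 − 17c) − (56 − 29g) = −12 − 17c + 29g.
- P(lower 95% limit above −12) = P(Z > 1.960 − (difference + 12)/3.763).

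| Share, cream / gel | Difference | False non-inferiority |
|---|---|---|
| 0 / 0 | −12.00 | 2.5% |
| 2% / 2% | −11.76 | 2.9% |
| 5% / 5% | −11.40 | 3.6% |
| 10% / 10% | −10.80 | 5.0% |
| 5% / 10% | −9.95 | 7.9% |
| 10% / 5% | −12.25 | 2.1% |

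The rate rises above 2.5% when 29g exceeds 17c, that is, unless the cream share is more than about 1.7 times the gel share (29/17 = 1.71).

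**5. The same with partial users.** Suppose instead that the misclassified subjects are the 9-of-14 kind and lose effect in proportion to missed days (5/14 = 35.7%). Replacing c and g by 0.357c and 0.357g gives about 2.9% (5% in both arms), 3.2% (10% in both) and 3.9% (5% cream, 10% gel).

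**The case against.** **A blank is not proof of a missed dose.** Protocol 8.3 and 8.4 speak of product applied and do not say how to read an empty diary day. A reader might infer that the SAP overturns the protocol's definition, or that nine entries and five blanks are by themselves non-adherent under 8.4. The documents support neither: SAP 4.2.3 and 5.3 keep application as the criterion, and a blank may be a dose that was not written down. What stands is that the SAP resolves every such doubt in one direction.

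**The forms are unseen.** SAP 2.4.3 separates approved non-administration from missed administration, so the diary or its transcription captures at least some non-use explicitly. Listing 16.2.5.8 also includes dose documentation. If the form forces a daily yes or no, blanks may be rare. This limits how often the problem occurs; it does not supply the missing rule.

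**Other safeguards exist.** Compliance is asked about at visits, containers are weighed, and per-protocol exclusions are decided in a blind review with accountability and compliance listings planned. A silent stop could well be noticed, and the link from the 2.4.3 percentage to the per-protocol set is an inference. But no rule turns visit answers or grams into non-compliant days, and for the hypothetical strategy the link is explicit.

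**The error rates rest on assumed shares.** This is right. Complete non-use is the severe case, as step 5 shows, and one asymmetric case falls below 2.5%. A reader might infer from protocol 2.2, which describes current oil-based products as inconvenient, that gel users skip more often. The documents do not quantify skipping in either arm.

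**Counting every blank as missed has its own bias.** Protocol 6.3 lets cleared subjects stop at the investigator's discretion. If they leave the diary empty, a bare blank-equals-missed rule would remove the best responders. This stands, and the fix allows for it.

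**Conclusion.** The point holds as a defect in a stated default. SAP 2.4.3 and 4.4.2 treat every unreported day as applied, and SAP 5.3 carries that count into the 70% rule. The classification result is firm: with a 14-day denominator, the protocol's own non-adherent example scores anywhere from 64.3% to 100%, depending only on how many of the five misses are reported.

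Its practical size is unknown, because it depends on the diary and eCRF layout. The false non-inferiority figures are illustrations under assumed shares. They show the usual direction, which is anti-conservative unless unreported non-use is clearly more common with the cream.

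A reader might go on to infer that the primary result or the trial's error control is compromised. It is not: the primary analysis follows the treatment-policy strategy on all randomised subjects and does not use adherence, and SAP 5.3 keeps sensitivity analyses outside the testing hierarchy. Nor do the documents show that the confirmatory PTCS test fails for this reason; its validity rule concerns treatment in the 7 days before assessment and is not tied to the compliance percentage. What is weakened is the support that the hypothetical analysis, and probably the per-protocol analysis, can lend to the non-inferiority claim. The change should be made before unblinding.

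**What to change.** In SAP 2.4.3, for the 70% and 80% rules:
- Count a day with no recorded application, or one covered by an unreturned diary, as not applied.
- Exempt days within an investigator-approved stop (cleared subjects, protocol 6.3) documented in the diary, at a visit or in the CRF, until a recorded restart.
- Derive the percentage also for Weeks 4–6 and Weeks 6–8, which SAP 5.3 needs and 2.4.3 does not define.
- Report the number of blank days by arm.
- Repeat the hypothetical and per-protocol analyses with blanks counted as applied, and report both versions.

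If the eCRF holds only reported misses, use diary-return status per interval to flag uncovered days.

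**Cost.** SAP text and programming before unblinding, with no new visits or assessments. Diary return is already scheduled at Visits 2, 4, 5 and 6, and Listing 16.2.5.8 already covers the diary card and dose documentation. The stricter rule will remove some true users who forgot to write and will make the per-protocol set smaller; the paired analyses show how much this matters.

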2.4.4 Concomitant Therapies and Procedures

All therapies, including non-drug therapies, and procedures taken within 30 days prior to the start of and/or during the trial will be recorded at Screening and throughout the course of the trial. Information regarding the total daily dose, route of administration, start and discontinuation dates, location and indication are recorded.

All verbatim terms of drug and non-drug therapies will be encoded according to the WHO Drug Dictionary version Q4/2018 and classified by PT and primary Anatomic Therapeutic Chemical (ATC) class level 2. All verbatim terms of procedures will be encoded according to MedDRA version 22.0.

A therapy or procedure is *concomitant*, if not ending before or at Week 0 (Day 0, Visit 1) and not starting after the date of last study drug application. A therapy or procedure is post-treatment, if starting after the date of last study drug application.

Per ATC level 2 and PT, frequencies of subjects with at least one concomitant therapy and at least one post-treatment therapy will be presented by summary tables by treatment group and overall, respectively.

2.5 Baseline Characteristics

2.5.1 Baseline Disease Characteristics

All patients suffer from mild to moderate psoriasis vulgaris on the body. At screening and at randomization, the trial population is described by

- time in years since diagnosis, defined as the number of years from diagnosis to randomization at Week 0 (Visit 1),
- Fitzpatrick Skin Type class at Screening (Visit 0), classified as I = pale white skin, blue/hazel eyes, blond/red hair, skin always burns and does not tan; II = fair skin, blue eyes, skin burns easily and tans poorly; III = darker white skin that tans after initial burn; IV = light brown skin that burns minimally and tans easily; V = brown skin that rarely burns and tans darkly easily; or VI = dark brown or black skin that never burns and always tans darkly,
- previous psoriasis treatment per type of treatment,
- BSA involvement on the body and on the scalp at Week 0 (Visit 1),
- mPASI score at Week 0 (Visit 1),
- PGA on psoriasis severity on the body and the scalp at Week 0 (Visit 1),
- SGA on disease severity at Week 0 (Visit 1).

Baseline disease characteristics will be presented by summary tables by treatment group and overall. Baseline disease characteristics will also be presented per country and per site.

2.5.2 Demographics

At Screening, gender (male, female), year of birth, race (American Indian or Alaska Native, Asian, Black or African American, Native Hawaiian or Other Pacific Islander, White, other) and ethnic origin (Hispanic or Latino, not Hispanic or Latino) will be recorded. Age is derived in full years from birth to Screening.

Demographics will be presented by summary tables by treatment group and overall.

2.5.3 Concurrent Diagnoses and Medical History

Entries of medical history, including concurrent diagnoses and surgeries, are recorded with start and end times. Verbatim terms of conditions, diagnoses and surgeries will be coded according to MedDRA version 22.0 classified according to PTs and primary SOCs and presented in summary tables by treatment group and overall. Per primary SOC and PT, frequencies of subjects with at least one entry in the medical history and with at least one concurrent diagnosis will be displayed. An entry in the medical history is a concurrent diagnosis if ongoing at Screening.

2.5.4 Previous Therapies and Procedures

Among recorded therapies and procedures (cp. Section 2.4.4), a therapy or procedure is *previous* if started before Week 0 (Visit 1).

Per ATC level 2 and preferred name, frequencies of subjects with at least one previous therapy will be presented by summary tables by treatment group and overall.

2.5.5 Vital Signs, Height and Weight at Baseline

Systolic and diastolic blood pressure, pulse rate and body temperature at Week 0 (Visit 1), height and weight from physical examination at Week 0 (Visit 1) and the body mass index, derived as weight in kg divided by the square of height in meters will be presented by summary tables by treatment group and overall.

3 General Specifications for Analysis

